##### **3.1.1 Dose Limiting Toxicity (DLT)**

A DLT will be defined as any Grade 3 or higher toxicity that occurs during the initial 6-week period the subject is on treatment (i.e., the DLT evaluation period). Toxicity that is clearly and directly related to the primary disease or to another etiology is excluded from this definition. Since this trial also involves immunotherapy, immune-related AEs (irAEs) are defined as AEs of an immune nature (i.e. inflammatory) in the absence of a clear alternative etiology. In the absence of a clinically significant abnormality, repeat laboratory testing will be conducted to confirm significant laboratory findings prior to designation as a DLT. The following will be DLTs:

- Inability to reduce prednisone dose below 10 mg within 6 weeks (rather than 12 weeks) due to ongoing immune-related adverse reaction of Grade >1
- Any Grade 4 irAE not attributed to local tumor response (e.g., inflammatory reaction attributed to local tumor response or inflammatory reaction at sites of metastatic disease or lymph nodes)
- Any  $\geq$  Grade 3 colitis
- Any Grade encephalopathy
- Any  $\geq$  Grade 3 neurotoxicity
- Any  $\geq$  Grade 3 peripheral neuromotor syndromes
- Any Grade 2 or higher noninfectious pneumonitis irrespective of duration
- Any Grade 3 irAE, excluding colitis that does not downgrade to Grade 2 within 3 days after onset of the event despite optimal medical management including systemic corticosteroids or does not downgrade to  $\leq$  Grade 1 or baseline within 14 days

- Total bilirubin  $>1.5 - 3.0 \times$  ULN (Grade 2 Hyperbilirubinemia)
- ALT or AST  $>8 \times$  ULN
- ALT or AST  $>5 \times$  ULN for more than 2 weeks
- ALT or AST  $>3 \times$  ULN and
- ALT or AST  $>3 \times$  ULN and INR  $>1.5$
- ALT or AST  $>3 \times$  ULN with appearance of fatigue, nausea, vomiting, right upper quadrant pain or tenderness, fever, rash, and/or eosinophilia ( $>5\%$ )
- Any Grade  $\geq 3$  non-irAE toxicity that does not downgrade to Grade  $\leq 1$  or baseline status (for patients who entered the study with an existing laboratory abnormality) within 14 days
- Inability to receive  $\geq 75\%$  or more of scheduled study treatment (both Vicineum and durvalumab) during the first six weeks of the trial

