## **6 DATA COLLECTION AND EVALUATION**

### **6.1 DATA COLLECTION**

The PI will be responsible for overseeing entry of data into a 21 CFR Part 11-compliant data capture system provided by the NCI CCR and ensuring data accuracy, consistency and timeliness. The principal investigator, associate investigators/research nurses and/or a contracted data manager will assist with the data management efforts. Primary and final analyzed data will have identifiers so that research data can be attributed to an individual human subject participant.

All AEs, including clinically significant abnormal findings on laboratory evaluations, regardless of severity, will be followed until return to baseline or stabilization of event. Document AEs from the first study intervention, Week 1/Day 1, through 90 days after the last administration of the study intervention. After 90 days, only adverse events which are serious and related to the study intervention need to be recorded.

An abnormal laboratory value will be considered an AE if the laboratory abnormality is characterized by any of the following:

- Results in discontinuation from the study
- Is associated with clinical signs or symptoms
- Requires treatment or any other therapeutic intervention
- Is associated with death or another serious adverse event, including hospitalization.
- Is judged by the Investigator to be of significant clinical impact
- If any abnormal laboratory result is considered clinically significant, the investigator will provide details about the action taken with respect to the test drug and about the patient's outcome.

**End of study procedures:** Data will be stored according to HHS, FDA regulations and NIH Intramural Records Retention Schedule as applicable.

**Loss or destruction of data:** Should we become aware that a major breach in our plan to protect subject confidentiality and trial data has occurred, this will be reported expeditiously per requirements in section [7.2.1](#).

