#### **6.2.3 Response Criteria**

Patients will be evaluated every 3 months as per standard of care with cystoscopy. Biopsy will be done at PI discretion pending cystoscopic findings. Any biopsies done will be for clinical reasons to rule out tumor recurrence, however, extra biopsy material if available will be used for research purposes.

Evaluable for toxicity: All patients will be evaluable for toxicity from the time of their first treatment with vicineum or durvalumab. All observed toxicities will be tabulated using CTCAE v5.0.

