## **8 SPONSOR SAFETY REPORTING**

### **8.1 DEFINITIONS**

#### **8.1.1 Adverse Event**

Any untoward medical occurrence in a patient or clinical investigation subject administered a pharmaceutical product and which does not necessarily have a causal relationship with this treatment. An adverse event (AE) can therefore be any unfavorable and unintended sign (including an abnormal laboratory finding), symptom, or disease temporally associated with the use of a medicinal (investigational) product, whether or not related to the medicinal (investigational) product (ICH E6 (R2)).

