### **8.1.6 Adverse Events of Special Interest (AESI)**

An adverse event of special interest (AESI) is one of scientific and medical interest specific to understanding of the Investigational Product and may require close monitoring and rapid communication by the investigator to the sponsor. An AESI may be serious or non-serious. The rapid reporting of AESIs allows ongoing surveillance of these events in order to characterize and understand them in association with the use of this investigational product.

AESIs for durvalumab include but are not limited to events with a potential inflammatory or immune-mediated mechanism and which may require more frequent monitoring and/or interventions such as steroids, immunosuppressants and/or hormone replacement therapy. These AESIs are being closely monitored in clinical studies with durvalumab monotherapy and combination therapy. An immune-mediated adverse event (imAE) is defined as an AESI that is

associated with drug exposure and is consistent with an immune-mediated mechanism of action and where there is no clear alternate etiology. Serologic, immunologic, and histologic (biopsy) data, as appropriate, should be used to support an imAE diagnosis. Appropriate efforts should be made to rule out neoplastic, infectious, metabolic, toxin, or other etiologic causes of the imAE.

In the event of imAE or suspected imAE, the AstraZeneca study team may request relevant clinical information (including images) for those subjects who demonstrate the event, and may request the independent review by external experts based on the acquired clinical information.

AESIs observed with durvalumab include:

- Diarrhea / Colitis and intestinal perforation
- Pneumonitis / ILD
- hepatitis / transaminase increases
- Endocrinopathies (i.e. events of hypophysitis/hypopituitarism, adrenal insufficiency, hyper- and hypothyroidism and type I diabetes mellitus)
- Rash / Dermatitis
- Nephritis / Blood creatinine increases
- Pancreatitis / serum lipase and amylase increases
- Myositis / Polymyositis
- Neuropathy / neuromuscular toxicity (e.g. Guillain-Barré, and myasthenia gravis)
- Intestinal Perforations

Other inflammatory responses that are rare/less frequent with a potential immune-mediated etiology include, but are not limited to:

- Myocarditis
- Pericarditis
- Sarcoidosis
- Uveitis
- Other events involving the eye and skin
- Hematological events
- Rheumatological events
- Vasculitis
- Non-infectious meningitis

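### Section 6.1 decides whether a laboratory value is an AE without any CTCAE grade threshold, so an asymptomatic, untreated Grade 3-4 value can be left out of the Grade ≥3 toxicity tables on investigator judgement

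*Combined protocol and SAP*

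**What the plan says.** Four places bear on whether a laboratory value is counted.

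- Section 6.1, which governs data entry: "An abnormal laboratory value will be considered an AE if the laboratory abnormality is characterized by any of the following". The five conditions are "Results in discontinuation from the study"; clinical signs or symptoms; a need for treatment; "Is associated with death or another serious adverse event, including hospitalization"; and investigator judgement of significant clinical impact. A further bullet only asks for details of clinically significant results.
- Section 8.1.1 defines an AE to include "any unfavorable and unintended sign (including an abnormal laboratory finding), symptom, or disease temporally associated with the use of a medicinal" product, whether or not related. It sets no condition on symptoms, treatment or significance.
- Section 3.1.1: "A DLT will be defined as any Grade 3 or higher toxicity that occurs during the initial 6-week period". It then lists some liver criteria by value (bilirubin >1.5-3.0 x ULN, ALT or AST >8 x ULN) and others that depend on duration, INR or symptoms. It also provides for other etiology, repeat testing, and isolated asymptomatic Grade 3 electrolyte abnormalities.
- Section 8.1.6 names transaminase and creatinine increases as AESIs, and "Pancreatitis / serum lipase and amylase increases". It gives no thresholds.

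On reporting, 10.1 makes the primary endpoint the fraction of patients with adverse events. Sections 10.4.2 and 10.4.4 tabulate toxicities by grade and report DLTs by dose level. Section 6.2.3 adds: "All observed toxicities will be tabulated using CTCAE v5.0". None of these says whether a laboratory value that fails the 6.1 list is a toxicity.

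**The concern.** The same asymptomatic, untreated Grade 3-4 value can be an AE under 8.1.1 and an AESI under 8.1.6, yet have no objective route into the AE record under 6.1. Its entry then rests on one open-ended judgement by an investigator who knows the treatment, in a trial with no control arm.

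Safety is the primary objective, and laboratory immune toxicity is an expected effect of durvalumab. The protocol already uses AE grades to argue tolerability: the text ahead of the combination dose justification cites mostly Grade 3 or lower events as a reason to continue. A Grade ≥3 table whose laboratory content depends on judgement is weak support for that argument. Any omission can only lower the count.

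Expedited AESI reporting in 8.3 also starts from an event that is already an AE, so the same filter may act there.

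**Working it through.** The plan gives no figure to reproduce here. The check is to follow each kind of laboratory value through the protocol's own rules.

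| Value | Recognised in | Route into 6.1 |
|---|---|---|
| Asymptomatic Grade 3-4 lipase or amylase, no pancreatitis | 8.1.1; named in 8.1.6 | Appendix C says steroids are not indicated for modest asymptomatic rises (no grade is attached to modest). If nothing is treated: judgement only |
| Asymptomatic Grade 3 value considered non-immune | 8.1.1, regardless of causality | Appendix C calls for a hold. A hold is not on the 6.1 list: judgement only |
| Creatinine or ALT/AST meeting a Vicineum hold rule in 3.3.2 | 8.1.1; 8.1.6 names both | Hold only: judgement only. These thresholds are not grades, so the Grade ≥3 tables are affected only when the value is that high |
| ALT/AST >5 x ULN managed as immune-mediated | 8.1.1, 8.1.6; some also 3.1.1 | Appendix C calls for IV steroids: treatment condition met |
| Grade 2 bilirubin in the DLT window | 3.1.1 | 3.3.2 removes the patient from study: discontinuation condition met |
| Isolated Grade 3 electrolyte, reversed within 3 days | 8.1.1; not a DLT under 3.1.1 | Reversed by medical intervention: treatment condition met |

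The first three rows are the gap and the last three are not. Stopping study drug is also not the same as discontinuation from the study: 3.6.1 (off therapy) and 3.6.2 (off study) are separate lists, and a DLT appears only in the first.

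**Could 6.1 be non-exclusive?** It says if, not only if. But a non-exclusive list would filter nothing, and the same section speaks of following clinically significant laboratory findings as AEs. Either the list restricts 8.1.1 or it has no function, and the plan does not say which.

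**Is there a backstop?** Sections 6.2.3, 10.4.2 and 10.4.4 refer to toxicities without defining them for laboratory values. No laboratory table is specified, and 10.4.8 provides no individual data. The values themselves exist: the Study Calendar schedules hepatic, mineral, acute care and pancreatic panels throughout induction and every 2 weeks afterwards.

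**Scale.** Section 10.4.2 refers to 24 or more patients. One omitted patient is 1/24 = 4.2 percentage points; at the accrual ceiling of 40 (10.2) it is 1/40 = 2.5 points.

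For context only, assume that the durvalumab monotherapy rates apply, with expected patients = 24p and Pr(at least one) = 1 − (1 − p)^24:

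- Grade 3-4 ALT/AST increase, 69/3006 = 2.3% (14.1.2, Table 1): 24 × 0.02295 = 0.55 expected; Pr = 0.43.
- Grade ≥3 selected hepatic events, 113/1645 = 6.9% (1.2.1.2): 24 × 0.0687 = 1.65 expected; Pr = 0.82.

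These are rates of events already recorded as AEs in other trials, so they show how often such events might arise, not how many 6.1 would lose. The lost share is not given and could be anywhere from 0 to 100%.

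**The case against.** The strongest reply is that the protocol's management rules bring most serious laboratory values into 6.1 anyway. High ALT/AST handled as immune-mediated is treated with steroids, bilirubin in the DLT window leads to removal from study, and reversed electrolytes have been treated. This stands, and it narrows the gap to the first three rows of the table.

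A reader might infer more than the documents support, in four ways.

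- That 8.1.1, 3.1.1 and 8.1.6 all count laboratory values on the number alone. Only some liver items in 3.1.1 do. Section 8.1.1 requires an unfavorable and unintended sign, 8.1.6 gives no values, and 3.1.1 has qualifiers on etiology, confirmation, duration and electrolytes.
- That DLT counts would be lost. They are defined in 3.1.1 and reported in their own right by dose level, and nothing makes them pass through 6.1.
- That the primary any-AE fraction is materially understated. A patient drops out of it only if the laboratory value was the sole AE. Dysuria alone was reported in 60.9% in the phase 2 Vicineum trial (14.2.2.2), so few patients would be in that position.
- That one or two lost patients would be a large part of the Grade ≥3 count. That requires setting all-cause laboratory rates against the drug-related Grade ≥3 rate of 10.0% (24 × 0.100 = 2.4 patients). The matching all-cause rate is 49.8% (24 × 0.498 = 12.0 patients). Drug-related Grade 3 AST and GGT increases were 0.6% and 0.8%, or 0.14 and 0.19 patients in 24.

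The reply does not remove the residual gap. Nothing in section 10 says how an asymptomatic, untreated Grade 3-4 value enters the tables.

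**Conclusion.** The point holds in a limited form. Section 6.1 is narrower than 8.1.1, is not aligned with 3.1.1 or 8.1.6, and carries no grade threshold. An asymptomatic, untreated Grade 3-4 value can be left out of the Grade ≥3 toxicity tables by judgement, most clearly for lipase or amylase or where the only consequence is a dose hold. Exposure is greatest after the 6-week DLT window, when no separate DLT report captures the value.

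A downward bias is possible but not shown, and its size cannot be estimated from the documents. Each omitted patient is worth 4.2 points in 24. The any-AE fraction would barely change, assuming most patients have some other recorded AE. The conclusion assumes that the 6.1 list is meant to restrict what is recorded. If it is not, the text still needs to say so. The sample size and the DLT rule are unaffected. The correction is worth making because it is cheap and takes an open-label judgement out of the Grade ≥3 safety report.

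**What to change.** 1. In 6.1 and 8.1.1, state one rule for when a laboratory value is an AE, and say that it feeds 10.1, 10.4.2 and 10.4.4. Add that any value confirmed as a DLT under 3.1.1, or classed as an AESI under 8.1.6, is recorded as an AE.
2. In 10.4.2 and 10.4.4, add text such as: all laboratory values collected on study will be graded by CTCAE v5.0, and every treatment-emergent Grade 3 or higher value will be tabulated by patient and dose level, whether or not it was recorded as an AE under 6.1.
3. Leave DLT designation to 3.1.1, with its existing window and its etiology, confirmation and electrolyte provisions. The new table is for reporting. It should not feed de-escalation or treatment decisions, and moving every Grade ≥3 value into the DLT table would override 3.1.1.

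The cost is one paragraph and one programmed table from chemistry already drawn, with no added patient burden. It can be applied to patients already treated. The reported Grade ≥3 rate may come out slightly higher.

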### **6.2 DATA SHARING PLANS**

#### **6.2.1 Human Data Sharing Plan**

##### **What data will be shared?**

I will share human data generated in this research for future research as follows:

- Coded, linked data in an NIH-funded or approved public repository.
- Coded, linked data in BTRIS (automatic for activities in the Clinical Center)
- Coded, linked or identified data with approved outside collaborators under appropriate agreements.

##### **How and where will the data be shared?**

Data will be shared through:

- An NIH-funded or approved public repository. Insert name or names: [clinicaltrials.gov](https://clinicaltrials.gov), [dbGaP](https://dbgap.ncbi.nlm.nih.gov).
- BTRIS (automatic for activities in the Clinical Center)
- Approved outside collaborators under appropriate individual agreements.
- Publication and/or public presentations.

#### **When will the data be shared?**

- Before publication.
- At the time of publication or shortly thereafter.

#### **6.2.2 Genomic Data Sharing Plan**

Unlinked genomic data will be deposited in public genomic databases such as dbGaP in compliance with the NIH Genomic Data Sharing Policy.

#### **6.2.3 Response Criteria**

Patients will be evaluated every 3 months as per standard of care with cystoscopy. Biopsy will be done at PI discretion pending cystoscopic findings. Any biopsies done will be for clinical reasons to rule out tumor recurrence, however, extra biopsy material if available will be used for research purposes.

Evaluable for toxicity: All patients will be evaluable for toxicity from the time of their first treatment with vicineum or durvalumab. All observed toxicities will be tabulated using CTCAE v5.0.

#### **6.2.4 Evaluable for Objective Secondary Endpoints/Response**

Only those patients who have biopsy-proven disease present at baseline, have received at least one intravesical dose of Vicineum therapy and one intravenous dose of durvalumab, and have had their disease re-evaluated will be considered evaluable for response. These patients will have their response classified according to the definitions stated below.

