## **Design:**

- This is a Phase I, open-label study of the combination of durvalumab and Vicineum in subjects with high-grade NMIBC previously treated with BCG.
- All subjects will receive Vicineum intravesically and durvalumab systemically at the standard doses for both drugs as determined by Phase II trials for each drug, as no synergy or additive effect is expected for adverse events.
- Vicineum is administered in a 12-week Induction Phase followed by a Maintenance Phase for at least one year with an option for a total of up to 2 years of treatment. During the Induction Phase, Vicineum is administered once weekly for 12 weeks. During the Maintenance Phase, Vicineum is administered every other week. The dose of Vicineum is 30 mg in 50 mL of saline.
- Durvalumab 1500 mg is administered intravenously (IV) once every 4 weeks for 12 months with an option to continue therapy for an additional 12 months (total of 24 months) provided that patient is tolerating therapy and remains free of recurrent high grade NMIBC (see Treatment Period below). The dose of durvalumab is 1500 mg. If optional maintenance therapy continued in the second year, durvalumab 1500 mg will be administered intravenously once every 3 months to provide an immune boost.
- Vicineum will be given as monotherapy for 1 week followed by treatment with the combination of Vicineum and durvalumab starting week 2.
- In the initial six patients, three subjects at a time will enroll at these doses and schedules. Dose-limiting toxicity (DLT) for each subject will be determined during the initial 6-week

period that the subject is on treatment (i.e., the DLT period). When all subjects in the initial cohort have been on treatment through the DLT period, all available safety data will be considered in decisions to enroll additional subjects at this dose level, or to de-escalate the dose(s) of study drug(s), based on a standard “3 + 3” design. There will be no dose-escalations in this study. The dose of durvalumab will remain at 1500 mg every 4 weeks, and the dose of each intravesical Vicineum treatment can be reduced to 20 mg if the initial doses in combination induce DLTs.

- After the first six patients, an additional 18 subjects will be enrolled at the initial doses or at the reduced doses (if DLTs resulted in the first 6 patients) in order to obtain additional safety data, biomarker data and preliminary anti-tumor activity.
- Each subject’s course will consist of the following periods:

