### **3.1.2 Dose De-Escalation / Cohort Expansion**

- This trial will begin with a fixed dose of Vicineum 30 mg intravesical (Dose Level 1) administered once weekly for the first 12 weeks. Durvalumab administration will begin after 1 week of Vicineum monotherapy, at 1500mg IV once every 4 weeks.
- In the initial six patients, three subjects at a time will enroll at these doses and schedules (Dose Level 1). Dose-limiting toxicity (DLT) for each subject will be determined during the initial 6-week period that the subject is on treatment (i.e., the DLT period). When all subjects in the initial cohort have been on treatment through the DLT period, all available safety data will be considered in the decision to enroll additional subjects at this dose level, or to de-escalate the doses of the study drugs to Dose Level -1, based on a standard “3 + 3” design (see table below). There will be no dose-escalations in this study.

- After the first six to twelve patients, an additional 18 subjects will be enrolled at the highest dose level at which fewer than 2 of 6 subjects experienced DLT in order to obtain additional safety data and preliminary anti-tumor activity. Treatment at this level will continue as long as the cumulative fraction of patients experiencing DLT is < 1/3.

Dose De-Escalation Schedule	
Dose Level	Dose of IND Agent
Level 1	

• Durvalumab 1500mg IV every 4 weeks

• Vicineum 30 mg intravesically per dose*

Level -1	

• Durvalumab 1500mg IV every 4 weeks

• Vicineum 20 mg intravesically per dose*

\* Vicineum administered weekly during the first 12 weeks of the study, then every 2 weeks thereafter.

Dose de-escalation will follow the rules outlined in the Table below.

If 2 or more DLTs occur at dose level -1, then accrual to the trial will end pending an amendment to consider other dosing options to explore for safety before proceeding to explore efficacy.

Number of Patients with DLT at a Given Dose Level	De-Escalation Decision Rule
0 out of 3	Enter an additional 3 patients at same dose level
1 of 3	

Enter an additional 3 patients at Dose Level 1

• If 0 of these 3 patients experience DLT, enter additional patients at Dose Level 1

• If 1 or more of this group suffer DLT then enter up to 3 patients at the next lowest dose level. Reduce by 1

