### **10.3 POPULATIONS FOR ANALYSIS**

Modified intention to treat: all patients who receive at least one dose of the two drugs will be included in the statistical analyses performed.

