#### **10.4.3 Analysis of the Secondary Endpoints**

Efficacy: A DFS curve will be created using the Kaplan-Meier method based on all patients considered to be evaluable based on having received protocol treatment, provided that adequate patients are enrolled in order to address this following an amendment to increase accrual.

The response to treatment will be determined for patients who receive treatment; the response rate for those patients who are evaluable for response, along with a 95% two-sided confidence interval will be reported.

As another secondary endpoint, all the evaluable patients will have determinations of many immune parameters at baseline, 3 months, and 6 months. The changes in the parameters obtained from blood samples will be determined at baseline vs. 3 months, and baseline vs. 6 months. The changes in the parameters obtained from biopsies will be obtained from baseline vs. a single second biopsy at 6 months. As an illustration, we will assume that a total of 25 paired tests will be considered of equal, primary importance. Paired results from 24 evaluable patients, including those used in the initial run-in portion who are treated at the highest safe dose, will be formed and tested for a difference from zero using a two-sided 0.002 significance level paired t-test, to

allow an overall 0.05 significance level test, applying a very conservative Bonferroni adjustment to the set of approximately 25 paired comparisons. In practice, comparisons of the paired values will likely be performed using a Wilcoxon signed rank test instead of a paired t-test, and a Hochberg adjustment may be used instead of an overly stringent Bonferroni adjustment.

Another secondary objective is to evaluate the pharmacokinetic parameters of Vicineum obtained by urine samples. This will be a descriptive analysis and will report sample statistics such as mean, standard error, median, minimum, maximum and other descriptive measures only.

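### The response rate leaves out treated patients whose disease was never re-evaluated, a condition that section 10.3 does not contain and that tends to raise the rate

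*Combined protocol and SAP*

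**What the plan says.** Section 6.2.4 sets three conditions for the response set. The patient must have biopsy-proven disease at baseline, must "have received at least one intravesical dose of Vicineum therapy and one intravenous dose of durvalumab", and must have had a disease re-evaluation: "and have had their disease re-evaluated will be considered evaluable for response".

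Section 10.4.3 first says that response is determined in treated patients, but what it reports is narrower: "the response rate for those patients who are evaluable for response, along with a 95% two-sided confidence interval will be reported".

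Section 10.3 defines a single modified intention-to-treat population: "all patients who receive at least one dose of the two drugs will be included in the statistical analyses performed". It has no re-evaluation condition. Its dosing phrase can mean a dose of either drug or a dose of each.

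The toxicity set is defined separately in section 6.2.3: "All patients will be evaluable for toxicity from the time of their first treatment with vicineum or durvalumab".

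On timing, section 3.1.2 states "Durvalumab administration will begin after 1 week of Vicineum monotherapy", and section 6.2.3 states "Patients will be evaluated every 3 months as per standard of care with cystoscopy".

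The plan has no rule that scores a treated but unassessed patient as a non-responder, and no sensitivity analysis of response in all treated patients.

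**The concern.** Sections 6.2.4 and 10.4.3 use one set of patients and section 10.3 describes another. On either reading of the dosing phrase in 10.3, the re-evaluation condition is an addition.

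The condition also depends on what happens to the patient after treatment starts. About three months pass between the first Vicineum dose and the first planned cystoscopy, and the protocol has several exits in that time:

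- A dose-limiting toxicity in the first six weeks ends study treatment (3.6.1).
- One hepatic finding in that period leads to removal from the study, not only from treatment (3.3.2).
- Death, withdrawal from the study or entry into another trial ends follow-up (3.6.2).
- The monthly visits after treatment consist of history, examination and laboratory tests, with no cystoscopy listed (3.6).

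Patients who leave in these ways have mostly not benefited. Removing them from the denominator tends to raise the rate.

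The rate is secondary and unpowered, but it is already in use. Section 1.2.3 cites an interim 12-week response rate from this trial as a reason to continue after the durvalumab urothelial indication was withdrawn. Section 6.2.4.2 foresees comparing complete response in carcinoma in situ (CIS) with historical rates. Both uses need a stated denominator that does not depend on outcome.

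**Working it through.** **The plan's own figure.** Section 1.2.3 gives 5 responders among 12 patients, written as 40%. 5/12 = 41.7%, with a Clopper-Pearson 95% interval of 15.2% to 72.3%. The stated 40% is a loose rounding of this. The text does not say whether the 12 are all treated patients or only those re-evaluated.

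**Formula.** Let x be the responders, n the patients in the section 6.2.4 set, and k the treated patients left out because they were not re-evaluated. The plan reports x/n. With unassessed patients counted as non-responders, the rate is x/(n + k). Since k is zero or more, x/n is never below x/(n + k).

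**Range for k (assumption).** The documents do not give k. Section 10.2 sets an accrual ceiling of 40 against 24 evaluable patients plus a separate run-in of 6 to 12, with the surplus meant for a small number of inevaluable patients. With the larger run-in, 40 − 24 − 12 = 4 places remain; with the smaller, 40 − 24 − 6 = 10. I use 0 to 4 as the working range and 10 as an outer bound.

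**Results.** The right-hand columns keep the interim response proportion at the planned size, 10 of 24. This is an illustration, not a forecast.

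| k | 5/(12 + k) | Drop, points | 10/(24 + k) | Drop, points |
|---|---|---|---|---|
| 0 | 41.7% | 0 | 41.7% | 0 |
| 1 | 38.5% | 3.2 | 40.0% | 1.7 |
| 2 | 35.7% | 6.0 | 38.5% | 3.2 |
| 3 | 33.3% | 8.3 | 37.0% | 4.6 |
| 4 | 31.3% | 10.4 | 35.7% | 6.0 |

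At the outer bound of k = 10, 10/34 = 29.4%.

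**Against sampling error.** The 95% interval is 22.1% to 63.4% for 10/24, a width of 63.4 − 22.1 = 41.3 points, and 18.6% to 55.9% for 10/28. The shift for k up to 4 is at most 6.0 points.

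**Who actually leaves the denominator.** Recurrence is confirmed pathologically (6.2.4.1) and progression is a change of stage (6.2.4.3). Detecting either one is itself a re-evaluation, so those failures stay in. Section 3.6.1 keeps patients who withdraw from treatment only on study for further evaluation. The loss is therefore confined to patients who stop for toxicity, withdraw or die and have no later assessment of the bladder.

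**The durvalumab condition.** Durvalumab starts in week 2, so this condition can remove only patients who stop during the one-week lead-in. If 10.3 means a dose of each drug, it agrees with 6.2.4 on this point. The firm conflict is the re-evaluation condition.

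**The case against.** The strongest case against is that little turns on this. Response is a secondary, descriptive estimate in a phase I safety trial. No sample size, test or decision rule in section 10 uses its value. The evaluable set is prespecified and labelled. The disease-free survival curve in 10.4.3 rests on having received protocol treatment and is not affected. Losses may also be small: the Vicineum phase I study in section 1.2.2.2 had 61 evaluable of 64 subjects with 24 responders, so 24/61 = 39.3% against 24/64 = 37.5%, a difference of 1.8 points. That benchmark itself uses an evaluable denominator, so moving only this trial to all treated patients could create a different mismatch.

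Most of this stands, and it sets the weight of the point. It does not remove the conflict between 6.2.4 and 10.3, and a wide interval does not correct a bias that runs in one direction. Reporting both rates meets the comparability objection.

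A reader might also draw three stronger conclusions, which the documents do not support:

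- **That the safety denominator is contradictory.** Section 6.2.3 admits every patient from the first dose of either drug, and 10.4.2 and 10.4.4 evaluate all patients for toxicity. Separate response and toxicity sets are not a contradiction. What remains is loose wording in 10.3.
- **That exclusions carry the combination past the single-agent result of 39% to 40%.** That figure (section 1.2.2.2, trial update) is a 3-month complete response rate in CIS. This trial also enrols high-grade Ta and T1 disease, so an overall response rate is not comparable with it, and any crossing would rest on assumed counts.
- **That every early failure drops out.** Detected recurrence and progression stay in, as shown above.

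**Conclusion.** The point holds as a modest one. The denominator in 6.2.4 and 10.4.3 excludes treated patients who were never re-evaluated, 10.3 states no such condition, and the exclusion tends to raise the reported rate.

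The size cannot be derived, because the number excluded is not given. On the assumption of 1 to 4 exclusions, a 10/24 rate is overstated by 1.7 to 6.0 points relative to the all-treated rate; with none excluded, the two rates are the same. These figures also assume that unassessed patients are scored as non-responders, which is a convention, not an observation. A patient who received only Vicineum and was later found in complete response would move the rate the other way. The power calculations in section 10.2 are unaffected.

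**What to change.** In sections 6.2.4, 10.3 and 10.4.3:

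1. Make the main response rate the number of responders divided by all patients with qualifying baseline disease who received at least one dose of Vicineum. Count any patient without a disease re-evaluation as a non-responder, and give the 95% interval on this denominator.
2. Report the rate in the present 6.2.4 set as a sensitivity analysis, and list each excluded patient with the reason.
3. Reword 10.3 so that it says plainly whether a dose of either drug or a dose of each is meant, and so that it agrees with the toxicity set in 6.2.3.
4. State the denominator whenever the interim rate in section 1.2.3 is cited.

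The cost is wording and one extra line in the results table. No new patients, visits or data are needed. The downside is that the reported response rate may be a few points lower.
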